## **DOCUMENT HISTORY**

NAME	DATE	VERSION	DESCRIPTION
20170630_ZIKAction_ZIKAction unique ZIKA-VT statistical analysis plan_V0.1	26/06/2017	1	First draft
20170630_ZIKAction_ZIKAction unique ZIKA-VT statistical analysis plan_V0.2	29/06/2017	2	Internal review
20170630_ZIKAction_ZIKAction unique ZIKA-VT statistical analysis plan_V1.0	30/06/2017	3	Final version

Author: [name] (UNIVBRIS)

7

#### **DEFINITIONS**

**Bayesian inference:** method of statistical inference that allows combination of prior information on a population parameter with evidence from information contained in a sample to guide the inference.

**Congenital abnormalities:** birth defects, structural or functional anomalies that occur prior to birth and can be identified prenatally, at birth, or sometimes later in infancy.

**Consortium**: the collaborative research group of Partners formed to undertake the Project.

**Cross-reactivity:** the reaction between an antibody and an antigen that differs from the immunogen.

**Partner:** each beneficiary who is a signing part of the Grant Agreement under which the Project

is financed.

Project: ZIKAction Project, financed within the H2020 Research and Innovation Programme of

the European Union, under Grant Agreement No. 734857.

**Sensitivity:** the ability of a diagnostic test to correctly identify those with the disease.

**Specificity:** the ability of a diagnostic test to correctly identify those without the disease.

**Stakeholder**: a person, group or organization that has an interest in the Project.

**Vertical Transmission:** passage of disease causing agent from mother to child in the period immediately before and after birth.

#### **ABBREVIATIONS**

CHIKV: Chikungunya virus
DENV: Dengue virus
GA: gestational age
IgM: immunoglobulin M
IgG: immunoglobulin G
MI: maternal infection

PCR: polymerase chain reaction RCT: randomized clinical trial

Author: [name] (UNIVBRIS)

**SAP:** statistical analysis plan

VI: vertical infection

VTR: vertical transmission rate

WP: work package ZIKV: Zika virus

8

Author: [name] (UNIVBRIS)

9

#### 1. Introduction

#### 1.1 The role of Statistical analysis plans (SAPs)

SAPs are commonly used to prevent selective use of data and data dredging by requiring the statistical data analysis to be specified in advance of data collection. SAPs have become a fixed feature of randomized clinical trials (RCTs). Because RCTs are specifically designed and powered around a single hypothesis, with exposure variables and a single primary outcome that are readily defined, every statistical analysis can be specified in detail in advance. Pre-specified SAPs are widely regarded as being desirable for observational studies as well, but there is no generally agreed format. It is recognized, however, that there must be room for an exploratory hypothesis-forming element [1] rather than rigid adherence to testing pre-specified hypotheses. This is especially relevant for vertically acquired ZIKA infection, whose clinical spectrum remains to be defined, and where the interpretation of laboratory measures of exposure is still very uncertain.

#### 1.2 Outline of this document

We begin by defining the three sets of objectives of ZIKA-VT (Section 2). We then explain its relationship to ZIKA-PED and ZIKA-VID because the data collection processes for all these programs are inter-related (Section 3). In Section 4 we set out the properties that the SAP is designed to have in order to meet the requirements of ZIKA-SYN, which is to allow a joint statistical analysis of ZIKA-VT alongside data from other prospective studies of vertical transmission.

Section 5 gives a background on the issues arising in estimating the vertical transmission rate. We then set out the SAPs for each of the areas of study in turn. Basic analyses of vertical transmission and clinical outcomes appear in Section 6, and methods for the full analysis in Section 7. Section 8 covers population epidemiology; analyses of clinical outcomes in women infected in pregnancy are found in Section 9.

Due to the nature of arbovirus transmission, and issues with the serological and virological tests, the ZIKA epidemic raises problems that require extensions to standard statistical methods. In order to keep the overall narrative clear, the more technical material appears in Appendices.

At the same time, certain aspects of the ZIKA-VT protocol have not yet been finalized: in particular, the choice of diagnostic tests. ZIKV diagnostics is a rapidly moving area of research, and we expect there will be changes during the period of study in which tests will be used in field work. Further tests to identify maternal, congenital and post-natal pediatric infection will be carried out on stored samples prior to the "final" analysis. Inevitably, therefore, important elements of the SAP are somewhat generic.

D1.1 ZIKAction unique ZIKA-VT statistical analysis plans WP1 ZIKA-VT Author: [name] (UNIVBRIS)

10

#### 1.3 Levels of analysis

The vertical transmission component of ZIKA-VT is complex observational study, which can be analysed at many different levels. A "face value" analysis, for example, might tabulate the vertical transmission or congenital malformation outcomes by laboratory findings during pregnancy, categorized as "Any laboratory evidence of maternal infection" vs. "No evidence of maternal infection". A further elaboration would be to break the lab findings down by trimester of first +ve test.

A slightly more sophisticated analysis, instead of tabulating trimester of the first +ve test, would combine the data on the dates of the tests with information on test persistence, using a pre-specified set of rules, to derive a variable that can be interpreted as "most likely trimester of maternal infection". A still more detailed analysis would additionally take into account surveillance information on what viruses were circulating and at that time, as well as information on test sensitivity, specificity and cross-reactivity. Surveillance data may carry more information about the timing of infection than the tests results. This information would be used to assign a probability that maternal infection took place in the 1st, 2nd, or 3rd trimester. Note that the more "basic" analyses are not simply "initial" analyses: they are needed at every stage to maintain transparency, and serve as essential preliminaries to the more sophisticated analyses that will be needed.

The extra value contributed by the more sophisticated analysis depends primarily on the accuracy of diagnostic tests and the quality of information on test persistence. Calculations in *section 7.6* show that, given the accuracy of currently available diagnostic tests, quite complex analyses may be required to avoid very substantial biases in estimates of the single most important target parameter: the vertical transmission rate.

For this reason, and where appropriate, the SAP will specify both "basic" tables, as well as describing the more sophisticated analyses that will, certainly at our present state of knowledge, be necessary.

## 2. Objectives of ZIKA-VT

There are three sets of objectives.

(1). The main objectives of ZIKA-VT involve assessment of vertical transmission rate, and the sequelae of vertical transmission for the fetus and the live-born child.

The follow-up of many thousands of women through pregnancy creates an opportunity to answer two further sets of questions relating to: (2) the population epidemiology of ZIKV, DENV and CHIKV and (3) natural history of these infections in the infected mother.

#### 2.1 Objectives relating to vertical transmission

There are two distinct questions relating to vertical transmission answered by the studies in ZIKA-VT and additional data from ZIKA-PED. The first concerns the risk of in utero transmission of ZIKV among

Author: [name] (UNIVBRIS)

11

infected mothers, while the second addresses the risk of adverse outcomes of maternal infection in the fetus, newborn and developing child.

In more detail, the objectives are therefore to estimate the role of gestational age (GA) at maternal infection (ZIKV, CHIKV, or DENV) and other risk factors in determining:

- (a) The vertical transmission rate (VTR)
- (b) Outcome of pregnancy following maternal infection: Fetal development, abnormalities on ultrasound, and outcomes of pregnancy (live-birth, stillbirth, miscarriage); GA at delivery; birthweight; anthropometrics including small for GA; cranial disproportion, and
- (c) Pediatric outcomes following maternal infection: Frequency, type, and severity of adverse outcomes (for example: growth, neurological, neurodevelopmental, ophthalmological, and auditory outcomes) up to 2-4 years of age:

In addition, the impact of maternal infection on both outcomes of pregnancy and pediatric outcomes must be studied: (i) in the presence of *in utero* transmission, (ii) in the absence of *in utero* transmission

The key risk factors of scientific interest for VTR, and for type and severity of pregnancy and pediatric outcomes, are: occurrence of maternal symptoms such as rash; co-infection with other arboviruses during pregnancy; previous infection with the same or different arboviruses, other co-infections. We will also recognize the possibility that VTR and risk of severe outcomes may vary between the collaborating centers, even when these risk factors are taken into account. Variables reflecting socioeconomic class or level of education will be treated as potential confounding variables as they may be correlated with both outcomes and exposure to ZIKV.

The same analysis plan will be applied to ZIKV, CHIKV and DENV.

## 2.2 Objectives relating to the population epidemiology of ZIKV, DENV and CHIKV

- (i) The incidence and cumulative incidence of arbovirus infections in areas contributing data; the prevalence of co-infections; impact of previous infections
- (ii) The proportion of infections that are symptomatic, and the impact of previous infection with the same or other arboviruses.
- (iii) Alignment with national or regional surveillance data, to obtain population estimates of national or regional incidence of ZIKV, DENV, CHIKV whether symptomatic or not.

#### 2.3 Objectives relating to outcomes for the infected mother.

- (i) Spectrum of clinical sequelae following symptomatic and asymptomatic infections, and time from infection to the appearance of sequelae.
- (ii) Impact of pregnancy on symptoms at presentation, and on spectrum and timing of sequelae
- (iii) Impact of cofactors on symptoms at presentation, and on spectrum and timing of sequelae, including co-infection or previous infection with the same or different arboviruses.

Author: [name] (UNIVBRIS)

12

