#### 9.1.2 Loss to follow-up. See Table 8.

9.1.3 Natural history: risk factors for subsequent clinical outcomes. These analyses focus on the subsequent development of clinical sequelae, following the initial presentation. Because there are time-varying risk factors, including pregnancy and infection status, this is best analyzed as a synthetic case-control study, considering each clinical outcome in turn.

As an illustration, we consider persistent joint pain as an outcome. All cases of persistent join pain will be identified, along with the time since the initial symptom presentation. For each case as many controls will be identified, up to a maximum of 10 (this number may be revised subject to the distribution of risk factors). To qualify as a control, a woman must have been under observation longer

Author: [name] (UNIVBRIS)

30

than the matched case without ever having experienced persistent joint pain. Control women will also be matched for center and for age at recruitment to the study, if possible to the nearest one or two years.

Matched logistic regression will then be used identify the role of risk factors in the development of persistent joint pain, including: infection (ZIKV, DENV, CHIKV, or no infection), symptomatic presentation initially, pregnancy, previous infection, socio-economic status or educational status, and so on. Table 9 illustrates the form of the output from this analysis. It is too early to specify which variables should be used to control for in multivariate analyses, and some recoding of variables may be needed.

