### Table 8. Women's cohorts: Completeness of follow up

		Recruitment	1m	4m	9m	12m
	Number of women					
ZIKV	Contributing data					
	Number lost to Follow-					
	ир					
	Number of women					
DENV	Contributing data					
	Number lost to Follow-					
	ир					
	Number of women					
CHIKV	Contributing data					
	Number lost to Follow-					
	ир					
Not	Number of women					
infected	Contributing data					
	Number lost to Follow-					
	ир					

Author: [name] (UNIVBRIS)

41

[figure not shown]
Table 9. Women's follow-up study - Natural history subsequent to initial presentation. Risk factors for a single specified clinical outcome.

sted Adjusted (95% CI) Rel Risk (95% CI)		Control	Cases	Risk factor
·	•			Infection
				ZIKV
				CHIKV
				DENV
1.0 (ref)	1			No infection
			nset	Pregnant at symptom of
				Yes
1.0 (ref)	1			No
			come onset	Pregnant at clinical outc
				Yes
1.0 (ref)	1			No
				Initial symptoms
				Yes
1.0 (ref)	1			No
				Mother's Age
				<19
				20-24
				25-29
1.0 (ref)	1			30+
		x infection	 r to the inde	Previous infection, prior
				ZIKV
				CHIKV
				DENV
1.0 (ref)	1			No infection
ef)	1			CHIKV DENV

Author: [name] (UNIVBRIS)

42

Figure 1. Schematic influence diagram. Showing the relationships between data and parameters in an analysis of vertical transmission rate and risk of clinical outcomes of vertical transmission. Rectangles denote data and ellipses parameters. Subscript *i* denotes mother-child-specific items, (t) denotes dependency on gestational age. Mother-child data and parameters are outlined in red. Items outlined in green and green influence arrows apply only in analyses which include adjustment for sensitivity, specificity and cross-reactivity of persistence tests.

Author: [name] (UNIVBRIS)

43

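### The SAP makes the timing of maternal sequelae an objective, but its only sequelae analysis reports relative risks and includes no estimate of timing

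*SAP*

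**What the plan says.** Section 2.3 lists three maternal objectives, and each has a timing element. Objective (i) is "Spectrum of clinical sequelae following symptomatic and asymptomatic infections, and time from infection to the appearance of sequelae". Objective (ii) is "Impact of pregnancy on symptoms at presentation, and on spectrum and timing of sequelae". Objective (iii) asks the same of cofactors such as co-infection and previous infection.

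Section 9.1 plans four outputs: initial symptoms (Table 6), symptomatic versus asymptomatic presentation (Table 7), completeness of follow-up (Table 8), and risk factors for later clinical outcomes (Section 9.1.3, Table 9). Only the last concerns sequelae. Citing time-varying risk factors, Section 9.1.3 says that "this is best analyzed as a synthetic case-control study, considering each clinical outcome in turn". In its joint-pain example:

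- Cases: "All cases of persistent join pain will be identified, along with the time since the initial symptom presentation".
- Control number: "For each case as many controls will be identified, up to a maximum of 10".
- Control eligibility: "To qualify as a control, a woman must have been under observation longer" "than the matched case without ever having experienced persistent joint pain", with matching on center and, where possible, age.

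Matched logistic regression follows. Table 9, titled in part "Risk factors for a single specified clinical outcome", holds case and control counts with unadjusted and adjusted relative risks.

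**The concern.** The SAP states the objective and also fixes the analysis, and the two do not meet. Matching on follow-up time removes the main effect of time from the model, and the plan adds nothing that brings it back. No cumulative incidence, survival curve, median time or exposure-by-time term is named for mothers. Survival analysis appears in Section 10.2, but only for categorical pediatric outcomes.

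An analyst who followed Section 9.1.3 exactly would finish with no result for the timing parts of Section 2.3. A ratio near 1 for pregnancy could also be read as no effect when onset is much earlier or later in one group.

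**Working it through.** The SAP gives no figure on this point, so there is none to reproduce. The check has two parts.

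**1. Objectives against planned outputs**

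| Section 2.3 asks for | Section 9 provides |
|---|---|
| Time from infection to sequelae | Time from symptomatic presentation, recorded for cases; no summary of it planned |
| The same for asymptomatic infections | No time zero |
| Effect of pregnancy on timing | One relative risk per factor level, no time term |
| Effect of cofactors on timing | The same |

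For symptomatic women the origin matters little, because Section 7.4.1 places infection at symptom onset. Women without symptoms do need one: Table 9 has rows for no infection and for no initial symptoms, and neither group has a symptomatic presentation to count from.

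**2. Can one matched ratio carry timing information?**

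*Illustration 1.* Assumed, not in the SAP: two groups of 2,000 women, 12-month risk 20% in both, complete follow-up, onset spread evenly over months 0–3 in group A and months 0–12 in group B.

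- Risk by 3 months: A 20%; B 20% × 3/12 = 5%.
- Rate ratio in months 0–3: ln(1 − 0.20) / ln(1 − 0.05) = 0.2231 / 0.0513 = 4.35. After month 3, A has no events and B has the remaining 15 percentage points.
- Single ratio r, controls free of the outcome at the case's time. The average proportions still at risk are A 0.90 and B 0.975 before month 3, then A 0.80 and B 0.875. Setting A's events (0.20) equal to their expected number gives 0.20 = 0.25 × 0.90r/(0.90r + 0.975) + 0.15 × 0.80r/(0.80r + 0.875). At r = 1.09 the right side is 0.1254 + 0.0749 = 0.2003; at r = 1.08 it is 0.1248 + 0.0745 = 0.1993. So r is about 1.09.
- Simulation of the same setting: mean 1.10 for a full-cohort Cox ratio (95% of replicates 0.96–1.24) and 1.12 with 10 such controls per case. The ratio in months 0–3 was about 4.3.
- Controls who never have the outcome, as Section 9.1.3 words it: (0.20/0.80) / (0.20/0.80) = 1.00.

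*Illustration 2.* Simulation of the Section 9.1.3 design with 10 controls per case. Assumed: 4,000 women, half pregnant, 12 months of follow-up, 10% dropout, 20 replicates. Entries are mean matched ratios for pregnancy.

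| 12-month risk, non-pregnant v pregnant | Median onset (months), non-pregnant v pregnant | Never-case controls | Controls free at case's time |
|---|---|---|---|
| 10% v 20% | about 1.5 v 1.5 | 2.25 | 2.07 |
| 10% v 20% | about 9.3 v 9.3 | 2.25 | 2.09 |
| 15% v 15% | about 4.8 v 4.8 | 0.97 | 1.02 |
| 15% v 15% | about 1.5 v 9.3 | 0.96 | 0.86 |

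As a check on the never-case column, (0.20/0.80) / (0.10/0.90) = 2.25. The first two rows give nearly the same output although onset differs by almost 8 months. The last two rows both lie near 1, although only the last has a timing effect.

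**The case against.** The strongest reply is that the design is not at fault. Time-matched sampling is a recognised way to handle time-varying exposures. An exposure-by-time interaction can be estimated in matched logistic regression, and absolute risk can be recovered because the cohort and sampling fractions are known. A single Cox ratio on the full cohort would hide the timing effect just as well (1.10 against 1.12 above). All of this stands. A reader might infer that the objective cannot be answered, or that the matched study must be replaced. The SAP does not support either reading: the estimates are omitted, not ruled out.

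A reader might also infer a serious loss of precision from sampling controls. At the stated maximum of 10, approximate efficiency near a null effect is 10/11 = 91%. Nothing in the SAP shows that far fewer controls would be found: age matching applies only where possible, and the maximum may be revised.

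The context also softens the point. Section 9 describes the work as largely descriptive, joint pain and Table 9 are illustrations, and Section 10.4 treats all outcomes other than vertical transmission and severe outcomes as hypothesis-forming. A false confirmatory claim is therefore unlikely. But a descriptive natural-history study needs a description of onset over time more than most, and none is specified.

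**Conclusion.** The point stands as an omission that should be corrected. Section 2.3 promises timing in all three maternal objectives, and no planned output estimates it. Asymptomatic infections, which objective (i) names, and uninfected controls have no time origin in Section 9.1.3. Table 9 does address risk factors for the occurrence of each sequela, so that part of the objectives is covered.

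The mismatch rests on the SAP's text alone. The numbers rest on assumed risks, onset patterns and follow-up; they show the mechanism and do not predict this study's results. In those settings an overall ratio of 1.0 to 1.1 coexists with a ratio of about 4.3 in months 0–3.

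**What to change.** Add to Section 9.1.3, for each sequela:

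1. **Cumulative incidence from the estimated date of infection**, by virus, pregnancy status and initial symptoms, at the Table 8 time points (1, 4, 9 and 12 months), allowing for interval-censored onset and loss to follow-up. Where there were no symptoms, use the Section 7.4 distribution of infection date; for women infected after pregnancy, run the same calculation over their own follow-up. Give uninfected women an assigned index date by a stated rule.
2. **An exposure-by-time-since-infection term**, either in the matched model or in a full-cohort Cox model with time-dependent pregnancy and infection status. Report ratios by period as well as overall.
3. **The control definition**: state whether controls must be free of the outcome at the case's time or throughout follow-up, since the two estimate different ratios (2.07–2.09 against 2.25 above).

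Add a table shell for the cumulative risks. The matched analysis and Table 9 may stay for risk-factor ratios. If timing is not to be estimated, remove it from Section 2.3.

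The cost is SAP wording and modest extra analysis. Infection dates for asymptomatic women will be uncertain, and that uncertainty should be carried into the estimates. Table 8 is an empty shell, so confirm that onset dates of sequelae are recorded for all followed women.

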### 3. Relation to ZIKA-PED, ZIKA-VID and ZIKA-SYN

#### 3.1 Outcomes of postnatal pediatric infection: ZIKA-PED.

Follow-up of postnatal infections, both primary and secondary, are within the remit of ZIKA-PED. However, postnatal infection will also be observed in ZIKA-VT. The statistical analysis of clinical symptoms and outcomes following postnatal infection seen in ZIKA-VT will be considered as part of the main ZIKA-PED analysis. However, estimation of post-natal ZIKV incidence rates in the control groups, part of ZIKA-PED, may be used to assist in the analysis of vertical transmission rates (see below and *Appendix 5*).

By the same token, after the two-year follow-up specified in ZIKA-VT, further follow-up of the three ZIKA-VT birth cohorts – Vertically Infected (VI), Maternal Infection no VI (MI – No VI), and No Maternal Infection (No MI) – will be undertaken within ZIKA-PED. However, to answer the scientific questions about outcomes of vertical infection, the statistical analysis of outcomes of vertical transmission after 2 years will be regarded as being within the remit of the ZIKA-VT statistical analysis plan. The ZIKA-PED (prospective) SAP will focus on outcomes of post-natally acquired ZIKV, which will be observed in the MI-No VI and No MI cohorts.

#### 3.2 Evaluation of diagnostic methods: ZIKA-VID.

One of the tasks of ZIKA-VID is to evaluate the diagnostic tests to be used in ZIKA-VT. This comprises both tests undertaken to establish women's infection before and during pregnancy, and tests to establish fetal infection. The evaluation of virological and serological tests in this context consists in estimating their sensitivity, specificity, cross-reactivity (a particular cause of lack of specificity), and persistence. Persistence refers to the duration of a positive response – for example a positive PCR or IgM response – or the duration of a rising IgG response. The ZIKA-VID evaluation will look at the analytic sensitivity and specificity of the tests, but also their diagnostic sensitivity and specificity, which must take into account background incidence. The evaluation will be based on a combination of published literature, specific laboratory studies undertaken within ZIKAction, and information about tests gathered in the course of ZIKA-VT. There is a rapidly developing literature on properties of tests that will be kept under constant review as it bears on the choice of diagnostic algorithms that will be used both in ZIKA-VT field work, and choice of tests and algorithms that will be used in a final data analysis. An Expert Group on ZIKA Diagnostics will be formed to take decisions on both choice of testing methods, and interpretation of test results (see *Appendix 1*).

Although the evaluation of the persistence of PCR and IgM tests properly falls within the remit of ZIKA-VID, it will become clear below that the analysis of persistence cannot be isolated from the analysis of gestational age at maternal infection and the risk of vertical transmission. These analyses must be conducted simultaneously and, as a result, all are covered in the ZIKA-VT SAP (Sections 6 & 7). If they are not carried out simultaneously, this would lead to an analysis of test persistence that is not technically consistent with our analysis of VTR.

Author: [name] (UNIVBRIS)

13

Further, the ZIKA-VT work on population epidemiology will contribute information about the test sensitivity, specificity and cross-reactivity. An outline of methods for deriving this information from the ZIKA-VT data will be covered in the population epidemiology SAP (*Section 8.2*), but a fuller account will appear in the ZIKA-VID work package.

